APPENDIX A: MODIFIED POUCHITIS DISEASE ACTIVITY INDEX (MPDAI)

According to Shen et al.; 2003 35

Clinical Criteria Stool Frequency	Score
Usual post-op stool frequency	0
1-2 stools/day > post-op usual	1
3 or more stools/day > post-op usual	2
Rectal Bleeding	
None or rare	0
Present daily	1
Fecal Urgency / Abdominal Cramps	
None	0
Occasional	1
Usual	2
Fever (temperature> 100°F)	
Absent	0
Present	1
Endoscopic Criteria	
Edema	1
Granularity	1
Friability	1
Loss of vascular pattern	1
Mucus exudate	1
Ulceration	1

APPENDIX B: SF-36

36-Item Short Form Survey Instrument (SF-36)

RAND 36-Item Health Survey 1.0 Questionnaire Items

Choose one option for each questionnaire item.

1. In general, would you say your health is:
1-Excellent
2-Very good
○ 3 - Good
○ 5 - Poor
2. Compared to one year ago, how would you rate your health in general now?
2. Compared to one year ago, how would you rate your health in general now? 1- Much better now than one year ago
1- Much better now than one year ago
1- Much better now than one year ago 2- Somewhat better now than one year ago

The following items are about activities you might do during a typical day. Does **your health now limit you** in these activities? If so, how much?

	Yes, limited a lot	Yes, limited a little	No, not limited at all
3. Vigorous activities , such as running, lifting heavy objects, participating in strenuous sports	O 1	O 2	3
4. Moderate activities , such as moving a table, pushing a vacuum cleaner, bowling, or playing golf	O 1	O 2	3
5. Lifting or carrying groceries	 	O 2	3
6. Climbing several flights of stairs	 	O 2	3
7. Climbing one flight of stairs	 	O 2	3
8. Bending, kneeling, or stooping	 	O 2	3
9. Walking more than a mile	 	O 2	3
10. Walking several blocks	 	O 2	3
11. Walking one block	 	O 2	3
12. Bathing or dressing yourself	 	O 2	3

During the **past 4 weeks**, have you had any of the following problems with your work or other regular daily activities as a result of your physical health?

 13. Cut down the amount of time you spent on work or other activities 14. Accomplished less than you would like 15. Were limited in the kind of work or other activities 16. Had difficulty performing the work or other activities (for example, it effort) 	t took e	xtra	Yes 1 1 1 1 1 1 1 1 1	2 2 2 2 2 2
During the past 4 weeks , have you had any of the following proof other regular daily activities as a result of any emotional prob ed depressed or anxious)?		-		or
	Yes	No		
17. Cut down the amount of time you spent on work or other activities	 	O 2		
18. Accomplished less than you would like	 	O 2		
19. Didn't do work or other activities as carefully as usual	 	O 2		
20. During the past 4 weeks, to what extent has your physical has problems interfered with your normal social activities with fan groups? 1- Not at all 2- Slightly 3- Moderately 4- Quite a bit 5- Extremely				, or

Liraglutide therapy in patients with IPAA and chronic high bowel frequency

21. How much bodily pain have you had during the past 4 weeks ?
1-None
2-Very mild
○ 3-Mild
○ 4 - Moderate
○ 5 - Severe
○ 6 - Very severe
22. During the past 4 weeks , how much did pain interfere with your normal work (including both work outside the home and housework)?
(including both work outside the home and housework)?
(including both work outside the home and housework)? 1-Not at all
(including both work outside the home and housework)? 1- Not at all 2- A little bit
(including both work outside the home and housework)? 1-Not at all 2-A little bit 3-Moderately

These questions are about how you feel and how things have been with you **during the past 4 weeks**. For each question, please give the one answer that comes closest to the way you have been feeling.

How much of the time during the past 4 weeks...

	All of the time	Most of the time	A good bit of the time	Some of the time	A little of the time	None of the time
23. Did you feel full of pep?	 	O 2	3	 	 	 
24. Have you been a very nervous person?	 	O 2	3	4	 	 
25. Have you felt so down in the dumps that nothing could cheer you up?	O 1	O 2	3	4	 	O 6
26. Have you felt calm and peaceful?	 	O 2	3	 	 	O 6
27. Did you have a lot of energy?	 	O 2	3	 	O 5	O 6
28. Have you felt downhearted and blue?	1	O 2	3	4	 	 
29. Did you feel worn out?	 	O 2	3	 	 	O 6
30. Have you been a happy person?	 	O 2	3	 	 	O 6
31. Did you feel tired?	 	2	3	4	 	6
32. During the past 4 weeks , how me problems interfered with your soc						
1-All of the time						
2-Most of the time						
3 - Some of the time						
4-A little of the time						
5-None of the time						

How TRUE or FALSE is **each** of the following statements for you.

	Definitely true	Mostly true	Don't know	Mostly false	Definitely false
33. I seem to get sick a little easier than other people	 	O 2	3	4	O 5
34.1 am as healthy as anybody I know	O 1	O 2	3	4	 
35. I expect my health to get worse	O 1	O 2	3	0 4	 
36. My health is excellent	O 1	O 2	3	4	O 5

APPENDIX C: PROMIS MEASURE INCONTINENCE

According to Kochar et al. 48 In the past 7 days...

	1 = No days	2 = 1 day	3 = 2-3 days	4 = 4-5 days	5 = 6-7 days
31611 - How often did you have bowel incontinence—that is, have an accident because you could not make it to the bathroom in time?					
31621 - How often did you soil or dirty your underwear before getting to a bathroom?					
31631 - How often did you leak stool or soil your underwear?					

	1 = Never	2 = Rarely	3 = Sometimes	4 = Often	5 = Always
31641 - How often did you think you were going to pass gas, but stool or liquid came out instead?					

APPENDIX D: PROBE SCORE

PROBE, a 6-question measure of quality of life among patients with inflammatory bowel disease⁵⁰

In the past 7 days...

I found it hard to focus on anything other than my anxiety

- (5) Never
- (4) Rarely
- (3) Sometimes
- (2) Often
- (1) Always

I felt hopeless

- (5) Never
- (4) Rarely
- (3) Sometimes
- (2) Often
- (1) Always

How fatigued were you on average

- (5) Not at all
- (4) A little bit
- (3) Somewhat
- (2) Quite a bit
- (1) Very much

I am satisfied with my ability to meet the needs of my friends

- (1) Not at all
- (2) A little bit
- (3) Somewhat
- (4) Quite a bit
- (5) Very much

How much did pain interfere with work around the home?

- (5) Not at all
- (4) A little bit
- (3) Somewhat
- (2) Quite a bit
- (1) Very much

How would you rate your IBD activity?

- (5) Remission
- (4) Minimal symptoms
- (3) Mildly active
- (2) Moderately active
- (1) Severely active

Note: Scores for each response to an individual question are listed in parentheses

APPENDIX E: SUBJECT DIARY FOR POUCHITIS Instructions: Begin recording in your diary each night. You should record before going to bed and the answers should describe the preceding 24 hours. During the Date During the past 24 hours During the past 24 How many of During the past 24 hours how many bowel hours how many of these bowel past 24 hours movements did you your bowel how many of did you movements have? experience movements were liquid your bowel (Please provide number) fever higher contained blood? (BL; number), movements than 37.8°C (Please provide pasty (BP; were (100.0°F)? number) number) or preceeded by formed (BF (Please mark abdominal number) "yes" or "No") cramps or an urgent need to go to the bathroom? (Please provide number) Yes Day Night No 8 am-22 22pm-8 am pm Yes No Yes No Yes No Yes No Yes No Yes No

APPENDIX F: ADVERSE EVENT DIARY

Front pages of diary

Efficacy of GLP-1 receptor agonist therapy in patients with an ileal -pouch anal anastomosis (IPAA) and chronic high bowel frequency

Record of Side Effects

This diary is one way researchers will get information from you regarding any possible problems or side effects in this study.

- ❖ What you are going to do is simple. Just keep a record of any unpleasant thing that happens to you while you are in the study, before, during, and after we started the study therapy. We even want you to record things that do not seem to be part of the study therapy, at all.
- ❖ When do you start? When do you end? You will complete one entry per day starting with the first day of study treatment time as well as daily until the last phone visit of the trial is completed.
- What do you look for? What do you report? Any symptom or problem whether or not it may be from the medicine, stool therapy. This could include: fever, abdominal pain, a big belly, lots of gas, diarrhea, nosebleeds, and anything else you know is not quite right.
- What will you do? Starting with the first day of the study medication, you will report some of the specific things that have bothered you by checking the boxes in the diary (see below). You can also write any other problems that you may have had during that time.

How will you record it? Like this...

EVENT	DATE OF ONSET	INTENSITY	ACTION TAKEN	MEDICATION	DATE RESOLVED
Fever	3/1/12	3	Missed 2 days of school	Tylenol-200mg	3/3/12
Sore throat	3/5/12	1	None	None	3/6/12

OTHER SYMPTOMS

Record each symptom at its **worst** level for each day.

For example, a sore throat that starts at 'Grade 1" but increases to 'Grade 2' should be recorded as 'Grade 2".

Examples of Grades:

Grade 1 – Mild: I noticed the symptom. It did not keep me from doing my normal activities.

Grade 2 – Moderate: I noticed the symptom and it kept me from doing some of my normal activities.

Grade 3 – Severe: I really noticed the symptom and it kept me from doing activities that I wanted or needed to do.

	age day 0 (start of tria	l therapy)				
ubject ID:		_				
ate:/_ lighest tempe	/_ erature of the day:	Check I °F	nere is no sid	e effects pr	esent:	
Check if symptom present	Event	Date of Onset	Intensity	Action taken	Medications	Date Resolved
	Fever					
	Abdominal Pain					
	Diarrhea					
	Nausea/Vomiting					
	Blood in Stool					
	Other 1					
	Other 2					
	Other 3					
	Other 4					
rade 2 – Moder rade 3 – Sever rade 4 – Very s	noticed the symptom. It did rate: I noticed the symptom a se' I really noticed the sympto severe: The symptom made I intervention was needed to	and it kept me fr m and it kept m me unable to pe	om doing some le from doing ac erform basic self	of my normal a tivities that I was -care functions	anted or needed to do	

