 New start of biologics, antibiotics, steroids, anti-motility therapies (e.g. hyoscyamine, loperamide, atropine)

• Non - steroidal anti-inflammatories (NSAIDs) as long-term treatment, defined as use for at least 4 days a week each month

STUDY OUTCOMES

PRIMARY OUTCOME

Reduction of the mean of the 7-daily bowel frequency by 30% in week 4 and week 10.

SECONDARY OUTCOME

- Safety and Tolerability of GLP-1
 - Number of study patients, who discontinued therapy
 - Adverse events grouped by body system
 - Changes in laboratory values
 - Changes in nausea, appetite, abdominal pain and well being
- Change in bowel frequency during day (patient is awake from morning until bedtime) and during night (patient is asleep and has to get up because he has a bowel movement) comparing screening period to week 1, week 2, week 3 and week 4 during active treatment with liraglutide or placebo in period 1 or in period 2 (week 7, 8, 9 and 10).
- Change in clinical PDAI week 0 and week 4 and week 10

EXPLORATORY OUTCOMES

- Change in stool calprotectin from baseline
- Change in SF-36
- Change in PROMIS measures
- Change in PROBE score
- Change in body weight and experience of nausea, decreased appetite or increased abdominal pain
- Change in PDAI at week 6 or week 12 in patients responding to liraglutide therapy
- Change in bowel frequency during day (patient is awake from morning until bedtime) and during night (patient is asleep and has to get up because he has a bowel movement) comparing screening period to week 5 and 6 in period 1 or 11 or week 11 and 12 in period 2.

ASSESSMENTS/INDICES

In regard to when the assessments are performed please also refer to study visits and table study visits and assessments.

- Patient diary (performed daily): Bowel frequency during the day (6 am-6 pm) and night (6 pm -6 am) and recording of bowel movement consistency (liquid, pasty or formed)¹⁴
- Patient diary (performed daily): Timing of bowel movement in relation to meals (within 15 min, 30 min or >30 min)
- Modified pouch disease activity index (mPDAI)³⁵

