EXPECTED ADVERSE DRUG REACTIONS

Liraglutide (Victoza®) is a FDA approved drug for treatment of diabetes and obesity. The protocol uses the current version of US/FDA approved Prescribing Information or any updates hereof for assessment of expectedness. Diarrhea, nausea or vomiting, the more frequent ADR have not been reported to be severe in the available studies in patients treated with a GLP-1 receptor agonist for diarrhea or high ileostomy output. This may be due to pre-existing low GLP-1 levels in this patient population or in case of diarrhea the lack of the colon (ileostomy patients). 19, 26, 27

Common ADRs caused by liraglutide include the following:

- nausea
- diarrhea
- constipation
- vomiting
- headache
- dyspepsia
- fatigue
- dizziness
- abdominal pain

- abdominal distension/flatulence
- GERD
- gastroenteritis
- eructation
- UTI
- cholelithiasis
- lipase increase
- injection site reaction
- insomnia
- xerostomia
- asthenia
- anxiety
- tachycardia

HYPOGLYCEMIA MONITORING, HYPOGLYCEMIC PROTOCOL AND REPORTING FORM

Hypoglycemia can occur in patients without concomitant treatment with a sulfonylurea drug or other drugs used to treat diabetes. There is currently no requirement to measure glucose levels in non-diabetic patients while being treated with liraglutide therapy for weight loss. Previous single center series in patients with ileostomy have not revealed an increased risk of hypoglycemia while treated with drugs like liraglutide. However, since this type of drug has not yet been evaluated in patients with an ileo- pouch anal anastomosis, patients will measure daily glucose levels before breakfast.

All study patients will be provided with a blood glucose (BG) meter including auxiliary supplies as well as instructions for use. The subjects will be instructed in to measure blood glucose fasting before breakfast daily, how to use the device and how to fill out the daily glucose protocol. The glucose diary will be reviewed at every study visit.

HYPOGLYCEMIC PROTOCOL AND REPORTING FORM

At randomization, all study patients will be instructed in symptom recognition and handling of hypoglycemia. Symptoms of hypoglycemia will be explained which may be hunger, shakiness, nervousness, sweating, dizziness or light-headedness, sleepiness, confusion, difficulty speaking, anxiety, weakness.

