- Type of treatment provided by other person (i.e., oral carbohydrates, glucagon, IV glucose or other)
- Were symptoms alleviated after administration of treatment?

If the hypoglycemic episode fulfils the criteria for an SAE then an AE form and a safety

information form will be completed.

DOCUMENTATION AND REPORTING OF ADVERSE EVENTS

The patients will be instructed to contact the investigator, if any serious or unexpected AE occurs, so that appropriate action can be taken.

Moreover, the investigator must ask at each follow-up visit a generally worded question without searching for any special symptoms, e.g. "Has your state of health worsened since we last met?" If the answer to this question is "no", no further questions will be asked. If the answer to the question is "yes", the investigator will document the nature, time, severity, seriousness and duration as well as the causality of the AE. For each AE a specific AE documentation form will be provided to the investigators. In case of an AE, this should be completed by the physician as an initial report. The report must contain a detailed description of the symptoms observed and the concomitant treatment administered. Furthermore, the investigator must comment on a possible causative relationship between the AE and the trial medication. Each AE must be followed until it is resolved or can be explained satisfactory.

The following has to be documented for each AE:

- Nature of the event
- Time of onset: date, time
- Concomitant treatment: product (generic name), indication, dosage, dosage interval, presentation, mode of administration, administration regimen
- Duration of the AE
- Severity
- Seriousness
- Causality
- Outcome

SEVERITY

The severity is evaluated as follows:

- 1. Mild: event/symptom does not interfere with normal daily activities
- 2. Moderate: event/symptom interferes with normal daily activities
- 3. Severe: event/symptom prevents normal daily activities

Causality

The relationship between an AE and the study medication is classified according to the WHO classification:

Certain

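### The adverse event diary keeps text from another study, and its tick boxes name only 4 of the 22 liraglutide reactions that the protocol lists; several others depend on unprompted reporting.

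*Combined protocol and SAP*

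**What the plan says.** Safety and tolerability form Aim 2 and a secondary outcome, reported partly as "Adverse events grouped by body system". The Expected Adverse Drug Reactions section opens its list with "Common ADRs caused by liraglutide include the following" and gives 22 entries.

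The patient-facing instrument is the diary in Appendix F. Its front page carries a title for this trial: "Efficacy of GLP-1 receptor agonist therapy in patients with an ileal -pouch anal anastomosis (IPAA) and chronic high bowel frequency". Its instructions nevertheless ask for "Any symptom or problem whether or not it may be from the medicine, stool therapy", and the worked example reads "Missed 2 days of school" with 2012 dates, in a trial whose age criterion is over 18 years. The daily page has five named tick boxes (fever, abdominal pain, diarrhea, "Nausea/Vomiting" as a single box, and blood in stool) and four blank lines for other events. The instructions also invite the patient to write down anything else.

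The other main route is the visit or phone contact. Under Documentation and Reporting of Adverse Events the investigator asks "a generally worded question without searching for any special symptoms"; if the patient says no, the enquiry stops. Coordinators also review the same diary at each contact.

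**The concern.** The diary is not a purely open instrument. It already prompts for chosen symptoms, so the choice matters. Most of the boxes repeat disease symptoms that the subject diary in Appendix E collects every day for the clinical mPDAI. Most of the reactions that the protocol itself expects from the drug have no box. Constipation is an obvious one to ask about for a drug meant to slow transit, and it has none.

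Nausea and vomiting are separate entries in the protocol's list but share one box, so a tick does not show which occurred.

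At stake is how complete the adverse event record is in a 10-patient proof-of-concept study meant to inform a larger trial. A symptom that the patient is not asked about, and does not think to mention, never reaches the safety table.

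**Working it through.** The plan gives no figure to reproduce here; the check is a count.

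**Step 1. Match the five boxes (Appendix F) to the 22 listed reactions and to the four clinical mPDAI items (Appendix A).** Those items are stool frequency, rectal bleeding, "Fecal Urgency / Abdominal Cramps" and fever.

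| Diary box | Listed reactions covered | Clinical mPDAI item |
|---|---|---|
| Fever | none | fever (same) |
| Abdominal pain | abdominal pain | urgency/cramps (close) |
| Diarrhea | diarrhea | stool frequency (close) |
| Nausea/vomiting | nausea, vomiting | none |
| Blood in stool | none | rectal bleeding (same in substance) |

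Boxes covering a listed reaction: 3 of 5. Reactions covered: 1 + 1 + 2 = 4 of 22. Without a box: 22 − 4 = 18. Boxes matching or nearly matching an mPDAI item: 4 of 5.

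**Step 2. Sort the 18 by what else in the protocol might pick them up.**

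- Partly picked up elsewhere (6): distension/flatulence (the diary instructions mention an enlarged belly and gas); fatigue (PROBE and SF-36); dizziness, anxiety and asthenia (the hypoglycemia form names dizziness, anxiety and weakness); tachycardia (heart rate at site visits).
- Mainly a laboratory finding or a diagnosis, so ill-suited to a daily tick box (4): gastroenteritis, UTI, cholelithiasis, lipase increase.
- No prompt as a reported event (8): constipation, headache, dyspepsia, GERD, eructation, injection site reaction, insomnia, xerostomia.

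Check: 6 + 4 + 8 = 18. Two entries in the last group are qualified. Stool frequency and consistency are recorded daily, so constipation is measured indirectly, though not labelled as an event. Gas in the diary instructions might be read to include belching. None of the sources in the first group is set up as an adverse event checklist.

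**Step 3. What incomplete capture does.** Suppose a fraction c of true cases is recorded, equally under both treatments and with no false reports. Then

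recorded difference = c × (true risk on liraglutide − true risk on placebo).

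Counts fall under both treatments and the difference shrinks by the factor c. Its direction does not change.

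**Step 4. Illustration only.** Neither the incidence nor the capture rates come from the documents. If a reaction truly affects 30% of 10 patients on liraglutide, the chance of recording no case is (1 − 0.30c)^10:

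- c = 0.9: 0.73^10 = 4%
- c = 0.7: 0.79^10 = 9%
- c = 0.5: 0.85^10 = 20%
- c = 0.3: 0.91^10 = 39%

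This shows that capture can matter at n = 10. It does not show which value of c applies.

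**The case against.** The strongest reply has four parts.

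1. **Several reactions do have other sources.** A reader might infer from the boxes that nothing else asks about the remaining 18. That would be wrong, as Step 2 shows. Change in nausea is also a named tolerability outcome with its own visual analogue scale, so the merged box is not its only measure. This part stands and narrows the point. The scale, however, has no stated assessment weeks and no row in the visit table, and vomiting has no separate prompt. Skin is examined at site visits, but that finds only an injection site reaction present on the day.

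2. **Diarrhea and abdominal pain are themselves listed reactions.** A reader might infer that only one box concerns the drug. Three do. This stands.

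3. **The form is the same under both blinded treatments.** A reader might infer a tilt in favour of liraglutide, because disease symptoms are prompted and many drug reactions are not. The documents do not support that: non-differential loss attenuates, and prompting for diarrhea and abdominal pain could equally raise liraglutide's counts. This stands against any claim of directional bias.

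4. **Open elicitation is a deliberate choice.** For the visit question it is, and the protocol says so. It does not settle the diary, which already solicits named symptoms; only the selection is poorly matched to this drug.

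The four open lines, the daily entry and the invitation to write anything also reduce the risk. They do not remove it.

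**Conclusion.** The point holds as a risk. The diary keeps wording from another setting, and its boxes name 4 of 22 listed reactions. Headache, dyspepsia, reflux, injection site reaction, insomnia, and constipation as a reported event depend on unprompted reporting; eructation and dry mouth appear to be in the same position. The consequence is possible incomplete capture under both treatments, with lower counts and possible attenuation of a true difference.

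Three stronger readings are not supported. The documents do not state the form's origin, so its descent from a stool-therapy study is an inference from leftover wording. They do not show that reactions will in fact be missed. They also establish neither a bias towards liraglutide nor its size: the percentages in Step 4 rest wholly on assumed inputs. The attenuation argument itself assumes equal capture under both treatments, which blinding makes reasonable but does not guarantee.

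This is a modest, inexpensive improvement to the safety data for Aim 2. It does not undermine the design.

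**What to change.** In Appendix F:

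- Replace the reference to the medicine and stool therapy with the study injection, and replace the school-absence example.
- Split nausea and vomiting into two rows.
- Add rows for patient-perceivable reactions already on the protocol's list: constipation, bloating/gas, heartburn/belching, headache, dizziness, tiredness, injection site reaction, racing heart. Insomnia and dry mouth would stay on the open lines unless given rows on the same ground.
- Keep the existing boxes and the four open lines.

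In the safety analysis, add one sentence: prompted and volunteered events are tabulated separately by treatment.

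The named rows go from 5 to 6 with the split, then to 6 + 8 = 14. The cost is one revised page before first use, a few more boxes for the patient each day, and somewhat higher event counts under both treatments. The treatments, visits, efficacy endpoints and sample size are unchanged.
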